AIM 1: Determine the effect of HAMS-AB on the gut microbiome profile and SCFA production in children with recently diagnosed T1D. We *hypothesize* that HAMS-AB consumption will shift the gut microbiome to microbial populations that are capable of HAMS-AB fermentation and increase SCFA production. Twelve youths (11-17 years old) will consume HAMS-AB or follow the standard of care recommended diabetic diet daily for [49,50] 4 weeks and then cross over after a 4-week washout period. DNA will be extracted from fecal samples obtained followed by 16S RNA sequencing for gut microbial community analysis at baseline and at each visit during the study period [32, 33]. SCFAs will be analyzed using standard methods [36, 37].

AIM 2: Determine the effect of HAMS-AB on glycemia and β -cell function and health. We *hypothesize* that the prebiotic HAMS-AB will improve overall glycemia including reducing glycemic variability in recently diagnosed persons with T1D. We will compare glycemic/ β -cell measures pre/post intervention with HAMS-AB and between the intervention and control groups. We will measure glycemia using HbA1c, average glucose and glucose variability using continuous glucose monitoring (CGM) [38-40]. We expect to see an improvement in glycemia in response to HAMS-AB intake. We will assess β -cell function using mixed meal tolerance (MMTT)-derived C-peptide measures. We *expect* that measures of β -cell stress/death will show improvement following the use of HAMS-AB. We will determine β -cell stress using proinsulin/C-peptide (PI:C) ratios [41]. We will assess β -cell death by differential methylation of proinsulin (INS) DNA [42].

Upon successful completion of this pilot study, we expect to assess the effect of prebiotic administration on the gut microbiome profile, SCFA production, glycemia and β -cell function in humans with T1D. The knowledge generated by the proposed research will provide critical experimental information needed to substantiate a fully powered study.

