34 STUDY ENDPOINTS

The primary outcome assessment will be to assess changes in the gut microbiome profile in response to HAMS-AB. Secondary outcome measures will be changes in SCFA production, changes in glycemia, pro-insulin to C-peptide ratios as a marker of β cell ER stress. Other β cell stress markers including unmethylated insulin DNA will also be measured. We will also examine glycemic outcomes and β cell function as assessed by responses to MMTT, although given the variability in these measures in other reported studies of new-onset T1D [43] we do not expect to be adequately powered in this small trial to see significant differences in these outcomes.

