6.3 SCHEDULE OF EVENTS

Study Phase	Screening	Baseline- Intervention	Washout	Crossover- Intervention	Follow-Up	Early Termination Visit
Visit Number	1	2	3	4	5	
Visit Window		≤30 days after Visit 1	+/- 3 days 28 days after Visit 2	+/- 3 days 28 days after Visit 3	+/- 3 days 28 days after Visit 4	
Informed consent/Accent	X					
Inclusion/Exclusion criteria	X					
Historical Data/Demographics*	X					
Pancreatic Autoantibodies †	X					
Random C-peptide concentration††	X					
Randomization		X				
Pregnancy test**	X	X	X	X	X	X
Current Medical data***		X	X	X	X	X
Pubertal Tanner staging with physical exam	X					
Ht/Wt measurement and vitals	X	X	X	X	X	X
Supervised CGM insertion (and training, if applicable on use) †††		X		X		
C-peptide by 2-hr MMTT††††			X		X	X
HbA1c		X			X	X
Blood samples for biomarkers (PI:C and INS DNA)		X	X	X	X	X
Provision of HAMS-AB		X		X		
CGM download			X		X	X
Stool samples****		X	X	X	X	X
Whole blood for additional T1D testing		X	X	X	X	X
Serum and plasma for storage^		X	X	X	X	X
Adverse event assessment*****		X	X	X	X	X
Dietary Assessments*****		X	X	X	X	X
Verbal Diet recall	X					
Sampling of prebiotic	X					

Data Collection:

***Historical data:** Date of birth, sex, Race/Ethnicity, date of diagnosis of T1D.

**To be done in girls of reproductive potential.

*****Current Medical Data (All visits except screening):** Medication use including types of insulin, means of insulin administration, and total daily insulin dose (u/kg body weight, averaged over the 3 days prior to each study visit), use of other medications.

******Stool samples** will be collected at home using a kit (Zymo feces catcher and RNA/DNA shield fecal collection tubes) within 3 days of presentation to each visit.

*****Participants will be assessed for **safety** with questions regarding general well-being as well as specific questions to evaluate for adverse events. Participants will also be questioned about stool form and frequency, gastrointestinal symptoms, fevers, or infection.

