8.0 STATISTICAL CONSIDERATIONS

A sample size of 12 with a cross over design (i.e., 12 per arm) is considered adequate to estimate effect sizes for efficacy to aid in designing future trials for responses that are normally distributed [52]. Simple comparisons will be performed using chi-square for categorical variables and t-tests for continuous variables. Random attritions and failed screens will be replaced. An intention to treat analysis will not be appropriate given the crossover design. Adverse events will be presented as the proportion of each event seen. This is considered a minimal risk study with low risk for minor adverse events such as mild gastrointestinal symptoms that could be related to increased dietary fiber intake. Our primary outcome is changes in the gut microbiome profile. To determine the diversity and richness of the microbiome, we will calculate a diversity index for both the pre- and post-intervention time points for each recipient. Microbial sequence analysis and statistics will be analyzed using the Quantitative Insights into Microbial Ecology (QIIME) 1.8.0 software as previously described [53].

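### For outcomes sampled at the start and end of both periods, the plan uses no baseline covariate; comparing post-minus-pre changes would give about 1.2 to 1.8 times the variance with 12 participants

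*Combined protocol and SAP*

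**What the plan says.** Section 8.0 (Statistical considerations) gives the primary outcome as "Our primary outcome is changes in the gut microbiome profile". Section 3.4 (Study endpoints) has "The primary outcome assessment will be to assess changes in the gut microbiome profile in response to HAMS-AB". The only quantity described is an index: "we will calculate a diversity index for both the pre- and post-intervention time points for each recipient". The method is one sentence: "Simple comparisons will be performed using chi-square for categorical variables and t-tests for continuous variables". No covariate, period term or mixed model appears.

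For the secondary outcomes, Section 3.4 says "Secondary outcome measures will be changes in SCFA production, changes in glycemia, pro-insulin to C-peptide ratios". Aim 2 in Section 1.2 compares glycemic and β-cell measures "pre/post intervention with HAMS-AB and between the intervention and control groups". On size, Section 8.0 says "A sample size of 12 with a cross over design (i.e., 12 per arm) is considered adequate to estimate effect sizes".

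The schedule in Section 6.3 lists stool, and the row "Blood samples for biomarkers (PI:C and INS DNA"), at Visits 2, 3, 4 and 5. Those visits are the start and end of each period. HbA1c is listed at Visits 2 and 5 and the MMTT at Visits 3 and 5, apart from early termination. Study CGM sensors are placed at Visits 2 and 4 and read at Visits 3 and 5, so they record within the periods.

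**The concern.** Where an outcome has a baseline in both periods, an outcome worded as a change, with pre and post values and a t-test, is most naturally read as a t-test on post minus pre. In a crossover each participant already serves as their own control. Subtracting the period baselines therefore removes little further between-person variation and adds the noise of two more measurements.

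The stated purpose of the 12 participants is to estimate effect sizes for later trials, so the precision of the HAMS-AB versus control estimate is the main product of this pilot.

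There is also a possible bias. Section 3.1 intends to assess how durable the effect is after washout, so some effect at Visit 4 is contemplated. If it fades during the control period, a change score counts the fading as a fall under control.

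**Working it through.** **The plan's own figure.** Section 6.2 assigns 6 participants to each sequence: 6 + 6 = 12, each receiving both treatments, which agrees with 12 per arm. No alpha, power, SD or correlation is given, so nothing more can be reproduced. All correlations below are assumptions.

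**Set-up.** Let X be the within-participant difference in period baselines (Visit 2 minus Visit 4) and Y the difference in end-of-period values (Visit 3 minus Visit 5). Give X and Y the same variance V, and let θ be their correlation. Variances of the treatment estimate are then proportional to:

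- change scores: 2V(1 − θ)
- end-of-period values only: V
- end-of-period values with X as covariate: V(1 − θ²), times 1 + 1/(12 − 4) = 1.125 for estimating the slope with 12 participants in two sequences

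The ratio of change to covariate-adjusted variance is 2/(1 + θ) in large samples and 2/(1 + θ)/1.125 here.

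**Values of θ.** Under compound symmetry θ = 0. Under AR(1) with correlation r between adjacent visits, Cov(X, Y) = r − r³ and V = 2(1 − r²) in units of the outcome variance, so θ = r/2.

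| Structure | θ | Large sample | 12 participants |
|---|---|---|---|
| Compound symmetry | 0 | 2.00 | 1.78 |
| AR(1), r = 0.3 | 0.15 | 1.74 | 1.55 |
| AR(1), r = 0.6 | 0.30 | 1.54 | 1.37 |
| AR(1), r = 0.8 | 0.40 | 1.43 | 1.27 |
| Strong within-period correlation | 0.80 | 1.11 | 0.99 |

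The last row arises, for example, with correlation 0.9 within a period and 0.5 between periods: θ = (0.9 − 0.5)/(1 − 0.5) = 0.8. Simulation with 6 + 6 participants agrees: about 1.75 to 1.8 under compound symmetry, 1.24 to 1.54 under AR(1) with r from 0.3 to 0.8, and about 1.0 in the last case.

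**95% half-widths at r = 0.6, in SD units.** These use t = 2.228 on 10 df, or 2.262 on 9 df with the covariate.

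- Compound symmetry, V = 2(1 − 0.6) = 0.8. Change: 2.228 × √(1.6/12) = 0.81. Adjusted: 2.262 × √(0.8 × 1.125/12) = 0.62. End-only: 2.228 × √(0.8/12) = 0.58.
- AR(1), V = 2(1 − 0.36) = 1.28. Change: 2.228 × √(1.28 × 1.4/12) = 0.86. Adjusted: 2.262 × √(1.28 × 0.91 × 1.125/12) = 0.75. End-only: 2.228 × √(1.28/12) = 0.73.

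The adjusted interval is about 24% and 13% narrower than the change-score interval.

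**Carryover.** Let L4 and L5 be the fractions of the effect still present at Visits 4 and 5 in those given HAMS-AB first, and b the covariate slope. Averaged over the two sequences, the estimate as a multiple of the true effect is:

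- change: 1 + (L4 − L5)/2
- end-only: 1 − L5/2
- adjusted: 1 − L5/2 + b·L4/2

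| Illustrative residue (b = 0.3) | Change | End-only | Adjusted |
|---|---|---|---|
| Decaying: L4 = 0.3, L5 = 0.1 | 1.10 | 0.95 | 0.995 |
| Persistent: L4 = L5 = 0.3 | 1.00 | 0.85 | 0.895 |

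**The case against.** **The change score is inferred.** A reader might infer that the plan defines its outcomes as change from each period's own baseline. It does not. Computing an index before and after intervention does not fix what the t-test compares, and Section 3.4 lists PI:C without tying it explicitly to a change. This stands, and the point is therefore conditional.

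**Not every outcome is affected.** HbA1c, MMTT C-peptide and study CGM have no baseline in each period, so neither the change score nor the covariate is available for them. A single covariate also does nothing for a multivariate community profile. Both limits stand.

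**The size is assumed.** An inflation of 1.4 to 2 is tempting, but that is the large-sample ratio for θ from 0.43 down to 0. It ignores the cost of estimating a slope from 12 participants, and strong within-period correlation removes the loss altogether.

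**End-of-period values alone do about as well.** In both half-width examples they are slightly narrower than the adjusted analysis. That is true at low θ. The covariate protects where θ is higher: at 0.8 the adjusted variance is 0.36 × 1.125 = 0.41 of the end-only variance.

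**Carryover cuts both ways.** A reader might infer that incomplete washout always biases change scores upward. It does so only if the residue shrinks between Visits 4 and 5. With a persistent residue, change scores are unbiased and the other two estimates are too small. An interest in durability is not evidence that washout fails, and Section 3.1 supports its length by earlier designs.

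**Conclusion.** The point holds as a cheap improvement. For the diversity index, PI:C, INS DNA, and SCFA if measured on the same stool samples, the plan leaves the role of the period baselines open and includes no covariate. If changes are compared, the variance is about 1.2 to 1.8 times that of the covariate analysis with 12 participants, under compound symmetry or AR(1) with r from 0.3 to 0.8. Put another way, 12 participants would then carry the information of roughly 12/1.8 = 6.7 to 12/1.2 = 10. With much stronger within-period correlation the two methods are about equal, and adjustment is never materially worse than change scores.

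The case rests on precision. The carryover bias is a secondary, conditional argument. The documents give no correlation and no residue, so none of these figures is a property of the trial's data.

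**What to change.** In Section 8.0 (Statistical considerations) and Section 3.4, for these scalar outcomes only:

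- Make the HAMS-AB versus control estimate the within-participant difference in end-of-period values (Visits 3 and 5), adjusted for period, with the within-participant difference in period baselines (Visits 2 and 4) as a covariate.
- Keep the Aim 2 pre/post comparison under HAMS-AB as a supporting summary.
- State that this does not apply to HbA1c, MMTT C-peptide, study CGM or the multivariate community profile.

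The cost is wording and one degree of freedom. At worst (θ = 0) the interval is about 7 to 8% wider than with end-of-period values alone: √1.125 × 2.262/2.228 = 1.077. No visit, sample or participant is added.

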3.1 STUDY DESCRIPTION

This study will be a single center, controlled, randomized trial in young individuals newly diagnosed with type 1 diabetes. We are enrolling youth with new onset T1D with documented continued residual C-peptide production. Within 30 days of screening during which eligibility will be determined, subjects will have a 4-week treatment period with HAMS-AB or will be provided with guidelines on the generally recommended diabetic diet for youths with T1D [49, 50]. After a 4-week wash-out period the durability of effect will be assessed in those who received the prebiotic and during this washout period, both the study and control arm will be permitted to consume a regular diet. This design has been used in other studies of prebiotic administration with a 3–4-week intervention period and a 3–4-week washout phase [21, 32, 33]. Subjects will then cross over to either HAMS-AB or diet control for another 4 weeks.

A full dosing description can be found in section 6.2.

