32 STUDY DURATION

This study will screen up to 24 subjects at a single center (see Enrollment below). 12 subjects will be enrolled after meeting all eligibility criteria. If at any time during the study, a participant does not meet eligibility, participation in the study will be on hold until subject meets all eligibility criteria again. Participants may re-enter or re-enroll in the study if in the future, meet all eligibility requirements. Participants who re-enter or re-enroll will need to be reassessed for their starting point. Subjects who miss 20% of prebiotic doses (11 of 56 doses) will be replaced. The study will include the following periods:

- (1) Screening visit and eligibility determination (up to 30 days).
- (2) 4-week intervention period or diet guideline
- (3) 4-week washout period
- (4) 4-week intervention period or diet guideline.

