6.1 STUDY DESIGN

6.2 RANDOM ASSIGNMENT

Subjects will be randomly assigned (6 in each arm) to either HAMS-AB plus a recommended diabetic diet or control diabetic diet alone [49, 50] for the first 4 week of treatment period. After a suitable washout period during which participants do not need to follow the recommended diet or use the supplement, subjects will continue for 4 weeks after a cross-over. All participants will be expected to follow the guidelines for a healthy diabetic diet during the study period, except for during the 4-week washout period.

A computer-based randomization plan will be prepared by the principal investigator. The document will be kept by the study team for use. As a subject is screened and qualifies, he/she will be assigned in order of screening date on the computer-generated document. One master list will be maintained in a confidential central shared folder for use. Subjects will be replaced on an ongoing list if they drop out.

Participants will be instructed to consume HAMS-AB with food, such as apple sauce or oatmeal, in two divided doses at breakfast and dinner at a total daily dose to be calculated as has been previously described for children: 10g plus 1g per year of age daily [44]. The prebiotic will be dispensed by the Investigational Drug Services (IDS) at Indiana University.

HAMS-AB will be in the form of acetylated and butyrylated **HYLON® VII** corn starch.

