6.4 STUDY VISITS

Visit 1 – Screening

This visit will be at the hospital or research center. It will last approximately 1-2 hours and will include:

- Obtain informed consent/assent documents and determine inclusion and exclusion criteria
- Measurement of height and weight to determine BMI percentile eligibility and physical exam including pubertal staging
- Obtaining Vital signs (heart rate, temperature, blood pressure, and respiratory rate)
- Obtaining medical history
- Dietary assessment by verbal recall
- Obtaining blood sample (approximately 1.5 tablespoon) – Random non-fasting c-peptide, pancreatic autoantibodies if not previously done to confirm T1D diagnosis
- For female adolescents: urine will be collected for a pregnancytest
- Subject to sample prebiotic for palatability to ensure compliance

Visit 2 – Baseline-Intervention

This visit will be at the hospital or research center. It will last approximately 1-2 hours and will include:

- Measurement of weight and bedside nurse assessment such as general appearance, respiratory and cardiac assessment.
- Obtain vital signs (heart rate, temperature, blood pressure, and respiratory rate)
- Collecting a diet history (diary or questionnaire)
- Collecting Adverse Events (if applicable)
- Obtaining medical history and insulin use

Obtaining blood samples (approximately 2 tablespoons) – HbA1c, Serum biomarkers of beta cell stress and death (PI:C and INS DNA), other T1D testing, and serum and plasma for storage.

- Some of the blood will be stored for future T1D research use

- CGM placement and training for participants not currently using one.
- For female adolescents: urine will be collected for a pregnancytest
- Collecting stool samples prior to or the morning of the visit (a stool collection kit will be shipped to the participants once eligibility is confirmed)
- Study Randomization to either supplement or standard of care diabetes management and a diabetic diet.
– Supplement (HAMS-AB) will be provided and will be taken by mouth twice daily with food such as apple sauce or oatmeal as described in Section 6.2. Instructions will be provided for recommendations on a healthy diabetic diet.
- A new stool collection kit will be provided for the next visit

Visit 3 - Washout

This visit will be at the hospital or research center. It will last approximately 2-4 hours and will include:

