- Measurement of weight, assessment of CGM insertion sites, as well as bedside nurse assessment such as general appearance, respiratory and cardiac assessment.
- Obtaining Vital signs (heart rate, temperature, blood pressure, and respiratory rate)
- Collecting a diet history (diary or questionnaire)
- Collecting Adverse Events (if applicable)
- Obtaining medical history and insulin use
- CGM download
- For female adolescents: urine will be collected for a pregnancytest
- Collecting stool samples prior to or the morning of the visit
- Obtaining fasting blood sample (approximately 5 tablespoons) – Serum biomarkers of beta cell stress and death (PI:C and INS DNA), other T1D testing, and serum and plasma for storage and MMTT

- samples (see below), and serum and plasma for storage
 - Some of the blood will be stored for future T1D research use
- Completion of a mixed meal tolerance test (MMTT). See below.
- After completion of this visit, participants will be instructed to follow a regular diet with no supplement intake for the following 4 weeks and to follow standard diabetes care as instructed by their diabetes provider.
- A new stool collection kit will be provided for the next visit

Preparing for an MMTT

- Subjects will be asked to fast except for water for at least 10 hours prior to visit.
- Subjects will be asked to limit strenuous activity for at least 10 hours prior to visit.
- Subjects will be asked to consume at least 150 g of carbohydrates each day for 3 days.
- If subject experiences hypoglycemia, morning of the visit, subjects will be instructed to treat low blood sugar and to reschedule MMTT procedure.

MMTT Visit procedures

Blood glucose will be tested and the MMTT started if blood glucose <200 by 10:00am. Long-acting insulin may be taken per routine, but short acting insulin must not have been given within 2 hours of MMTT.

An IV catheter will be placed in the arm by trained nurses for blood drawing purposes. Blood will be drawn 10 minutes prior to drinking Boost, just prior to drinking Boost, 15, 30-, 60-, 90-, and 120-minute post Boost consumption. High Protein Boost will be measured to a dose of 6ml/kg body weight (maximum dose 360ml). Total volume of blood will be approximately (5 tablespoons) not to exceed 5ml/kg/day.

Visit 4 Crossover-Intervention

This visit will be at the hospital or research center. It will last approximately 1-2 hours and will include:

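### Section 8.0 writes out no HAMS-AB versus control contrast for the primary microbiome outcome; followed as a pre/post change in recipients, the estimate would mix supplement, instructed diet and time

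*Combined protocol and SAP*

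**What the plan says.** Section 3.4 (Study Endpoints) sets the primary outcome as to "assess changes in the gut microbiome profile in response to HAMS-AB" and names no comparator. Section 2.1 and Aim 1 name none either, although Aim 1 does describe the crossover and stool sampling at baseline and each visit.

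Section 8.0 (Statistical Considerations) has one sentence on how the primary outcome is computed: "we will calculate a diversity index for both the pre- and post-intervention time points for each recipient". Around it stand a general statement that continuous variables are compared by t-test, without groups, pairing or periods, and a reference to QIIME software and a cited paper. The same section counts the crossover as 12 per arm and gives the purpose as estimating effect sizes for future trials.

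A comparison with control is written out only in Aim 2, for glycemic and beta-cell "measures pre/post intervention with HAMS-AB and between the intervention and control groups".

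On diet, section 6.2 compares HAMS-AB plus a recommended diabetic diet with that diet alone. Participants are to "follow the guidelines for a healthy diabetic diet during the study period, except for during the 4-week washout period". At Visit 2 (section 6.4), where the supplement is first provided, "Instructions will be provided for recommendations on a healthy diabetic diet". After Visit 3, "participants will be instructed to follow a regular diet with no supplement intake for the following 4 weeks"; section 3.1 likewise says that in washout "both the study and control arm will be permitted to consume a regular diet". At Visit 4 the recommended diet is listed again for the control arm, and section 6.2 expects it of everyone outside washout.

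**The concern.** The primary outcome has a measurement rule but no stated comparison, and the rule can be read in two ways.

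- **Every participant, both periods.** The schedule in section 6.3 labels Visits 2 and 4 as intervention visits for everyone, and all 12 participants eventually receive HAMS-AB. The index would then exist before and after each period, but the plan still does not say how the two conditions are compared.
- **The HAMS-AB period only.** Section 3.2 lists each treatment period as a "4-week intervention period or diet guideline", which separates intervention from diet guideline. Pre/post change in recipients is then an uncontrolled change.

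On the second reading, the pre sample comes before both the supplement and the instructed diet, and the post sample follows both, whichever sequence the participant is in. The estimate then cannot separate the supplement from the diet or from time. A biased effect size would defeat the trial's stated purpose even if no hypothesis is ever tested.

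**Working it through.** **The plan's own figure.** Section 6.2 assigns 6 per arm: 6 + 6 = 12 participants, each receiving both conditions, so 12 per condition. This agrees with section 8.0. No alpha, SD, effect or power is given, so there is no sample-size formula to reproduce.

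**What each analysis estimates.** Let d be the HAMS-AB effect, and s1 and s2 the average diet-plus-time shift over the first and second treatment periods. With 6 per sequence and no carry-over:

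- Pre/post change in recipients = d + (s1 + s2)/2.
- End-of-period contrast. In the HAMS-AB-first sequence, Visit 3 minus Visit 5 has mean d + s1 - s2. In the control-first sequence it has mean -d + s1 - s2. Half the difference is d, so shifts common to both arms within a period cancel, even when s1 and s2 differ.

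**Size under assumptions.** Not in the documents: two-sided 5%, shifts in units of the between-person SD at a visit, and correlation rho between visits of 0.3 to 0.7. With d = 0 and s1 = s2 = s, the paired t-test has 11 df and noncentrality s x sqrt(12)/sqrt(2(1 - rho)). Example: s = 0.5, rho = 0.5 gives 0.5 x 3.464/1 = 1.732, and 35.3% positive.

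| Assumed shift | rho 0.3 | rho 0.5 | rho 0.7 |
|---|---|---|---|
| 0.1 SD | 5.8% | 6.2% | 6.9% |
| 0.25 SD | 10.3% | 12.4% | 17.6% |
| 0.5 SD | 26.7% | 35.3% | 53.2% |

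For unequal shifts of 0.1 and 0.5 SD, the pre/post bias is (0.1 + 0.5)/2 = 0.30 SD. In simulation (20,000 trials per setting, six correlation patterns), the pre/post test is positive in about 12-22% of trials. The period-adjusted contrast is positive in 4.8-5.3% of trials in every setting tried, with bias within about 0.006 SD, which is simulation noise.

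**Precision.** Half-width in SD = t(0.975, df) x sqrt(2(1 - rho))/sqrt(12), with 11 df for pre/post (t = 2.201; visits 4 weeks apart) and 10 df for the end-of-period contrast (t = 2.228; visits 8 weeks apart).

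| rho at 4 weeks, at 8 weeks | Pre/post | Contrast | Ratio |
|---|---|---|---|
| equal (0.5, 0.5) | 0.635 | 0.643 | 1.012 |
| 0.7, 0.6 | 0.492 | 0.575 | 1.169 |
| 0.5, 0.3 | 0.635 | 0.761 | 1.198 |
| 0.7, 0.5 | 0.492 | 0.643 | 1.307 |
| 0.7, 0.3 | 0.492 | 0.761 | 1.546 |

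A contrast of changes from period start was 14-42% wider than the end-of-period contrast in the six simulated patterns. Using the period-start values as a covariate instead was 0-7% wider than using none in those patterns, and about 3% narrower only under a steeper fall in correlation.

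**Carry-over.** Suppose fractions c4 and c5 of d persist to Visits 4 and 5 in the HAMS-AB-first half.

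- Pre/post change is unaffected: no participant has had HAMS-AB before the pre sample.
- End-of-period contrast = [(d - c5 d) + d]/2 = d(1 - c5/2). With d = 0.5 SD and c5 = 0.3: 0.5 x 0.85 = 0.425 SD.
- Contrast of changes = [d - (c5 - c4)d + d]/2 = d(1 + (c4 - c5)/2). It is unaffected if persistence is constant, and too large if the effect is present at Visit 4 but gone by Visit 5.

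**The case against.** The strongest reply is that a controlled comparison is plainly intended. The trial is a randomised crossover, Aim 1 describes it for the microbiome, section 8.0 counts 12 per arm, and a diversity index is a continuous variable to which the t-test sentence applies. The disputed sentence may only say what is calculated and when. This largely stands. A reader might infer that the plan commits to an uncontrolled pre/post analysis or disregards its control period, and the documents do not support that. What remains is that the contrast is implied and not written, so an analyst could choose among pre/post, end-of-period and change-score analyses after seeing the data.

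Second, all magnitudes are assumed. The documents give diet instructions, not how far intake or diversity would move. The diet is described as standard of care and participants are 4-36 months from diagnosis, so the real shift may be slight. This also stands. In a pilot without a stated alpha the bias matters more than the false-positive rates, which serve only to illustrate scale.

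Third, the remedy is not free or unique. The endpoint is worded as change, so a contrast of changes is as legitimate as one of end-of-period values, and unlike pre/post change either contrast can be distorted by carry-over. Section 3.1 itself contemplates persistence by planning to assess durability after washout. This stands and shapes the fix. Finally, the figures concern a single index, whereas the outcome is a profile; the lack of a stated contrast applies to any summary of it.

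**Conclusion.** The point holds as a gap in the specified analysis that should be fixed, not as a flaw in design or data. No section states a HAMS-AB versus control contrast for the primary outcome, and the only sentence specific to it describes pre/post values. That a pre/post change in the HAMS-AB period would combine supplement, diet and time follows from the visit structure and does not depend on any assumed number. How large the bias would be is unknown: at an assumed 0.1 SD it is minor, and at 0.5 SD the test is positive in 27-53% of trials with no supplement effect. A reader might infer that the trial's primary result will be biased. That would require both the recipients-only reading and a material shift, and the documents establish neither.

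**What to change.** In section 8.0, state that the primary estimate is the within-participant HAMS-AB versus control contrast with period in the model. Prespecify one form, either end-of-period values (Visits 3 and 5) or changes from period start (Visit 2 to 3 and Visit 4 to 5). If end-of-period values are chosen, say whether the period-start values enter as covariates. Label the pre/post change in recipients descriptive. Use the Visit 4 samples to report whether the effect persisted through washout in the HAMS-AB-first half, which fits the durability assessment already planned in section 3.1.

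No visit or sample is added: section 6.3 already schedules stool at Visits 2 to 5. The statistical costs should be named:

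- One degree of freedom.
- For end-of-period values, an interval about 1% wider than pre/post if correlations are equal, and 17-55% wider in the assumed cases where correlation falls with time. The change form was wider still in the simulated patterns.
- Sensitivity to carry-over: the end-of-period estimate falls by half of whatever fraction of the effect persists to Visit 5, and the change form is distorted if persistence differs between Visits 4 and 5.
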